A study on fexinidazole concentrations in milk was conducted on lactating female albino rats after the administration of 800 mgeq/kg of [14C]-fexinidazole. Radioactive drug-related material was detected in milk at a concentration similar to that in plasma and in blood. Exposure to the radioactive drug-related material was approximately 80% of that measured in plasma, in terms of both C_{max} and AUC values.

On the basis of these findings, the same extent of exposure can be expected in breastfed human newborns. Median and maximum plasma exposure to M2, the main metabolite, observed in women participating in the FEX004 study were 529 and 930 μ g•h/mL respectively. This corresponds to a plasma M2 concentration of approximately 22 to 39 μ g/mL, from which it can be inferred that the concentration in breast milk will be from 18 to 31 μ g/mL. Thus, for newborns with a mean weight

Confidential Page 22 of 83

of 3 kg who consume around 500 mL of breast milk per day, this corresponds to total exposure to M2 in the range of 9.0 to 15.5 mg/day, i.e. 3.0 to 5.2 mg/kg.

Nevertheless, as a precautionary measure, pregnant women will be eligible to participate in the study only once they have reached the second trimester of pregnancy and will not be eligible for treatment on an out-patient basis.

The target population will also include patients whose health status is not as good as in earlier studies, within medically acceptable limits, as this is likely to be the case for some patients who will be treated in the future. Thus, the eligibility criteria for patients in the study are less strict that those in earlier studies on fexinidazole with, in particular, deletion of some criteria based on laboratory tests and on bodymass index (BMI).

As in early studies, in particular DNDiHATFEX006, children under 6 years of age will not be part of the target population for practical reasons related to the size of the tablets and difficulty in swallowing them.

Lastly, the study will provide additional laboratory data at 3 months and 6 months to supplement the existing laboratory safety database, with a particular focus on haematological and hepatic functions.

2. Study Objectives and Endpoints

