6.7.2. Procedures at Follow-up Visits at 3, 6, 12 and 18 months

Whether the patient is being treated in hospital or as an out-patient, the following procedures will be performed at Follow-up Visits at 3, 6, 12 and 18 months:

- Collection of blood and/or lymph samples for testing for parasites;
- Collection of CSF for WBC and detection of trypanosomes. At the 3-month follow-up visit, lumbar puncture will be performed only if indicated by the patient's clinical status;
- Collection of signs and symptoms of HAT, if any;
- Karnofsky Performance Status;
- Vital signs: body temperature, blood pressure, heart rate and respiratory rate;
- Physical and neurological examinations;
- Urine pregnancy test for women of child-bearing potential, only at 3-month and 6-month visits;
- Collection of SAEs
- Collection of non-serious AEs assessed as related to fexinidazole;
- Laboratory safety assessments (see Appendix 3 Laboratory Tests; p 75) when possible, samples will be collected in the morning from patients in the fasting state:
 - Haemoglobin;
 - Haematology: WBC, platelet count;

Confidential Page 38 of 83

o Biochemistry: albumin, ALP, ALT, AST, BUN, chloride, creatinine, glucose, potassium, sodium, calcium, total bilirubin, bicarbonates and total protein.

Laboratory safety assessments will be performed at the 12-month and 18-month visits only if indicated by the patient's clinical status.

In the event that a patient moves house or is travelling away from home during the follow-up period, the Investigator accompanied by any necessary study team members may travel to the patient's new place of residence in order to perform one or more follow-up visits.

The patient could also attend one or more follow-up visits in another investigational centre or in a satellite centre. The patient would then be managed by the Investigator in the other investigational centre or by the Coordinating Investigator at the PNLTHA.

The site investigator and his/her study team can also travel to the satellite site to monitor the patient.

In that case, the Investigator in the patient's original investigational centre should inform the Coordinating Investigator and the person in charge of monitoring that a visit is planned to take place in a different investigational centre.

Data collected at such visits will then be sent, within a reasonable timeframe after the visit, to the patient's original investigational centre in order to be recorded in the CRF.

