6.8.3. Follow-up on AEs

Any AE must be followed up until it resolves, until the Investigator considers it to be "stable" or "chronic", or until the end of the patient's participation in the study, i.e. until the end-of-study page of the CRF for the patient has been completed.

If the AE is a clinically significant laboratory test abnormality, a repeat test is to be performed 2 to 4 days later and then at regular intervals until the value returns to normal or to the baseline level.

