	Type of test	Specific test	Number of samples	Quantity per sample (approx.)	Total volume per visit
		Woo/CTC	1	100 µL	
	Parasitology	Thin/thick blood smear	1	≤ 300 µL	≤ 400 µL
		mAECT (±BC)	1	5 mL	5 mL
Blood		Haemoglobin	1	20 µL	
Біооц	Haematology (M3 and M6)	WBC	20 µL	170 ul	
		Platelet count	1	10 µL	170 μL (capillary
		Differential WBC	1	20 µL	blood ¹⁾
	Biochemistry (M3 and M6)	14 parameters	1	100 µL	
Lymph	Parasitology	If lymph nodes detectable			
CSF	Parasitology	Modified Single Centrifugation	1	4 mL	4 mL
Urine	Pregnancy (M3 and M6)		1	5 mL	5 mL

Quantity of blood required for PK analyses

Entire study

	Type of test	Number of samples	Quantity per sample (approx.)	Total volume
Blood	PK	6	2mL	12 mL

All haematological and biochemical analyses can be performed using a single finger-prick with a Tenderlett® device or similar.

Confidential Page 77 of 83

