Appendix 7 - Schedule of Study Events

Table 5 – Schedule of Events - Patients treated in hospital

Protocol-planned procedures and forms to be completed	Screening					Treatm	ent per	iod		In-ho	spital Follo	Follow-up period			
Timepoint →	D-15 to D-1	D1	D2	D3	D4	D5	D6	D7	D8	D9	D10	D11 (EoT)	D12	D13-D18 (EoH)	3 – 6 – 12 – 18 months
Rapid Diagnostic Test or CATT	х														
Detection of parasite in blood and/or lymph	Х											х			Х
Informed consent (before any additional medicines or study-specific procedures)	х														
Lumbar puncture (parasite and white blood cells in CSF)	х														x ¹
Pretreatment of helminthiasis ²	х														
Rapid Diagnostic Test and/or thick blood smear for diagnosis of malaria and, if necessary, treatment ²	х														
Karnofsky Performance Status	х											Х			Х
Inclusion and exclusion criteria	х														
Demographic data	х														
Medical history	х														
Signs and symptoms of HAT	х											х			Х
Vital signs ³	х								X ⁴			х		х	Х
Physical and neurological examinations	х								X ⁴			Х		х	Х
Haematology and biochemistry	х											х			X ⁵
Urine analysis	х											х			
Urine pregnancy test	X (D-1)											х			X (3 and 6 months only)
Triplicate ECG	x (D-1)				X D4 H4	X D4 H23	3					х			
Administration of fexinidazole		Х	Х	Х	Х	Х	Х	Х	Х	х	Х				
Blood sampling for PK analyses (specific patient groups)									X H3.15	Х Н3	X H3 H7.15	X D10H24	X D10H48		
Adverse event (AE) collection	X (if considered related to study participation)	х	х	х	х	х	х	х	х	х	х	х	х	х	X (If reasonable possibility of relation to treatment)
Serious adverse event (SAE) collection from signature of consent form to last study visit	х	Х	х	х	х	х	х	х	х	х	х	х	х	х	х
Collection of concomitant medication	х	Х	Х	Х	х	Х	х	х	х	х	Х	Х	х	Х	

Page 82 of 83

Confidential

¹ At 3 months, only if indicated by patient's clinical status.

² Treatment according to national guidelines.

³ Temperature, blood pressure, heart rate and respiratory frequency.

⁴ Only if indicated by patient's clinical status.

⁵ At 3 and 6 months. At 12 and 18 months only if indicated by patient's clinical status.

Protocol DNDi-FEX-09-HAT Version 3.0 Fexinidazole

Table 6 – Schedule of Events - Patients treated on an out-patient basis

Protocol-planned procedures and forms to be completed ${\sf Timepoint} \ \to $	Screening D-15 to D-1	Dispensing D0	Treatment period										Follow-up period	
			D1	D2	D3	D4	D5	D6	D7	D8	D9	D10	D11 (EoT)	3 – 6 – 12 – 18 months

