Rapid Diagnostic Test or CATT	х													
Detection of parasite in blood and/or lymph	x												Х	х
Informed consent (before any additional medicines or study-specific procedures)	х													
Lumbar puncture (parasite and white blood cells in CSF)	Х													x ¹
Pretreatment of helminthiasis ²	х													
Rapid Diagnostic Test and/or thick blood smear for diagnosis of malaria and, if necessary, treatment ²	х													
Karnofsky Performance Status	х												х	х
Inclusion and exclusion criteria	х													
Demographic data	х													
Medical history	х													
Signs and symptoms of HAT	х												х	Х
Vital signs ³	х												Х	Х
Physical and neurological examinations	х												х	х
Haematology and biochemistry	х												х	X ⁴
Urine analysis	x												Х	
Urine pregnancy test	X (D-1)												х	X (3 and 6 months only)
Triplicate ECG	X (D-1)												х	
IMP dispensing / Discharge from hospital		х												
Administration of fexinidazole			х	х	х	х	х	х	х	х	х	х		
Blood sampling for PK analyses													X D10H24 ⁵	
Assessment of understanding of instructions for treatment (questionnaire)		Х												
Treatment compliance (interview)													Х	
Acceptability of packaging (questionnaire)													Х	
Adverse event (AE) collection	X (if considered related to study participation)												X (interview)	X (If reasonable possibility of relatio to treatment)
Serious adverse event (SAE) collection from signature of consent form to last study visit	•													-
Collection of concomitant medication	х												X (interview)	

¹ At 3 months, only if indicated by patient's clinical status.

² Treatment according to national guidelines.

³ Temperature, blood pressure, heart rate and respiratory frequency.

⁴ Only if indicated by patient's clinical status.

⁵ Additional sampling for PK may be performed between Day 1 and Day 11 if the patient returns to the centre for an unscheduled visit

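### The out-patient schedule (Protocol Table 6, footnote 4) makes follow-up blood tests indication-only at every visit, contradicting Section 6.7.2 and Appendix 3, which plan them at 3 and 6 months

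*Protocol*

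**What the plan says.** Protocol Appendix 7 has one schedule for each treatment setting. In Table 6 (out-patients) a single column covers the 3-, 6-, 12- and 18-month visits. The haematology and biochemistry cell in that column carries footnote 4, under which the tests are done "only if indicated by patient's clinical status". The footnote names no visit, so it applies to all four.

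In Table 5 (in-patients) the same row carries footnote 5: "At 3 and 6 months. At 12 and 18 months only if indicated by patient" (the sentence ends with the reference to clinical status).

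The body text sets one rule for both settings. Section 6.7.2 opens with "Whether the patient is being treated in hospital or as an out-patient, the following procedures will be performed at Follow-up Visits", lists haemoglobin, haematology and biochemistry, and then adds: "Laboratory safety assessments will be performed at the 12-month and 18-month visits only if indicated". Appendix 3 labels both haematology and biochemistry M3 and M6 in its follow-up table and does not separate in-patients from out-patients. Section 1.6 gives the purpose: "the study will provide additional laboratory data at 3 months and 6 months to supplement the existing laboratory safety database", with haematological and hepatic functions named as the focus.

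**The concern.** Two parts of the current protocol give sites different instructions for the same patients at the same visits. Section 6.1 refers readers to Appendix 7 for the schedule, and no rule says which text prevails. A site using Table 6 as its checklist would take no routine blood panel from an out-patient after Day 11.

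Three things are at stake.

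- **Detection.** Section 1.4 reports liver-function reactions and transient, asymptomatic grade 3 and 4 neutropenia in a Chagas disease study of the drug. Tests triggered by clinical status are poorly suited to finding abnormalities without symptoms. The protocol does not give the timing of those events, so this is a reason for the planned panels and not evidence of missed cases.
- **The safety endpoint.** The grade 3 or higher adverse event endpoint (Section 2.2.2) includes clinically significant laboratory abnormalities and counts related non-serious events up to 18 months. If one cohort is tested routinely and the other only on indication, the chance of finding such events differs between them.
- **The laboratory tables.** SAP Section 8.8.3 presents month-3 and month-6 values, changes and shifts by cohort. Out-patient values gathered only on indication would come from a selected group.

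**Working it through.** The protocol states no figure to reproduce. The check compares the texts and then counts scheduled panels.

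**Step 1: the texts side by side**

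| Place | Setting covered | Routine follow-up visits | Indication-only visits |
|---|---|---|---|
| Table 6, footnote 4 | Out-patients | None | 3, 6, 12, 18 months |
| Table 5, footnote 5 | In-patients | 3, 6 months | 12, 18 months |
| Section 6.7.2 | Both, stated | 3, 6 months | 12, 18 months |
| Appendix 3 | Not split | M3, M6 | Not stated |
| Section 1.6 | Not split | 3, 6 months (data promised) | Not stated |

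**Step 2: could footnote 4 mean something narrower?** Elsewhere in the same column, limits to particular visits are written out. Footnote 1 restricts its condition to month 3, and the pregnancy-test row is limited to months 3 and 6. A footnote without such a limit therefore reads as applying to all four visits. All five Table 6 footnotes read as complete, so text lost in conversion is unlikely. Footnote 4 has the same wording as Table 5 footnote 4, which there governs the Day 8 vital signs and examinations. Carry-over from Table 5 is the likely cause, but that is an inference.

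**Step 3: routine post-baseline panels per out-patient**

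- Sections 6.6 and 6.7.2: Day 11 + month 3 + month 6 = 3.
- Table 6 as written: Day 11 = 1.
- Difference: 3 − 1 = 2 of 3 scheduled panels.

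**Step 4: how much earlier the last routine panel falls**

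- Table 6: Day 11, which is 10 days after Day 1.
- Section 6.7.2: the 6-month visit, with an acceptable leeway of 150 to 299 days after Day 1 (Protocol Table 2).
- Interval: 150 − 10 = 140 days to 299 − 10 = 289 days.
- Table 2 also accepts an end-of-treatment visit on Day 12 (11 days after Day 1). The interval is then 150 − 11 = 139 to 299 − 11 = 288 days, which changes nothing of substance.

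These counts cover scheduled panels only. The out-patient share of the 174 patients is not stated, so no study total is given.

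**The case against.** The strongest reply is that the intent is not in doubt. Section 6.7.2 names out-patients expressly and four places point the same way, so this is a clerical slip that a careful site would read past. The laboratory manual and the CRF, neither of which is available here, may prompt the month-3 and month-6 panels, and centralised monitoring (Section 11.5) looks for missing data. This shows which text to correct. It does not show that sites working from Table 6 did the tests.

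Several narrower points are fair:

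- Appendix 3 does not say that it covers both settings; it only makes no distinction. The explicit statement is in Section 6.7.2.
- The cohorts are not randomised, their adverse event windows already differ (Day 11 against Days 13 to 18), and no laboratory test between cohorts is planned. The by-cohort tables are descriptive, so the problem is how to read them and not a biased test.
- The timepoint list in SAP Section 8.8.3 includes Day 5, at which neither schedule plans a panel, so it is weak evidence of the intended schedule. It does show that month-3 and month-6 results will be tabulated by cohort.
- The Day 11 panel is routine in every version. For a clinically significant abnormality reported as an adverse event, Section 6.8.3 requires that "a repeat test is to be performed 2 to 4 days later and then at regular intervals until the value returns to normal" or to baseline. This protects patients whose abnormality is seen at Day 11, but not those whose abnormality arises later without symptoms.
- The SAP already shows N and missing counts (Section 7.4), a missing category in the shift tables by severity (Section 9.2.11) and visit attendance (Section 8.1). Gaps would be visible, but not whether they arose from selective testing.
- SAP Section 11 describes changes after database lock, so correcting the footnote may no longer alter what was collected. The reporting part of the remedy would still apply.

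**Conclusion.** The inconsistency is real and stands in the current protocol text. Taken literally, Table 6 makes out-patient haematology and biochemistry routine at 0 of 4 follow-up visits, against 2 of 4 under Section 6.7.2. That removes 2 of the 3 routine post-baseline panels for each out-patient at a site following it. The last routine panel then falls 140 to 289 days earlier (139 at the lowest if the end-of-treatment visit is on Day 12).

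This size is conditional. It assumes that a site followed Table 6 and not Section 6.7.2, which the documents do not show, and a site following Section 6.7.2 loses nothing. Retests under Section 6.8.3 are additional. The primary effectiveness endpoint and the sample size are untouched. The error should be corrected because it bears on planned safety data and costs almost nothing to fix, but it does not threaten the main result.

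**What to change.** Replace Table 6 footnote 4 with the text of Table 5 footnote 5: routine at 3 and 6 months, indication-only at 12 and 18 months. Table 6 then agrees with Section 6.7.2 and Appendix 3. If follow-up is still open, notify the sites.

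If data collection is complete, as SAP Section 11 suggests:

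- state in the study report which schedule sites followed for out-patients;
- give the number tested among month-3 and month-6 attendees, by cohort;
- interpret the by-cohort month-3 and month-6 laboratory tables in that light.

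The cost is one protocol footnote or, after data collection, one sentence and one small count table built from data that the SAP already tabulates.

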## 2. VERSION HISTORY

Version	Date	Author	Comment / changes
0.1	24/10/2016	[REDACTED]	Initial draft version (based on protocol version 1.0 dated of 10/08/2016 and CRF version 1.0 dated of 27/09/2016)
0.2	21/03/2017	[REDACTED]	Add comments from DNDi
0.3	12/12/2017	[REDACTED]	Add comments from [REDACTED] Version based on protocol version 2.0 dated of 17/03/2017)
0.4	22/03/2018	[REDACTED]	Add comments from [REDACTED]
1.0	27/04/2018	[REDACTED]	First approved and signed version
2.0	23/09/2022	[REDACTED]	Second approved and signed version. Included changes as requested by DSMB on 03-AUG-2022.
3.0	23/09/2022	[REDACTED]	third approved and signed version. Included changes on algorithms.

### 3. ABBREVIATIONS

Abbreviation	Description
AE	Adverse Event
ALT	Alanine Aminotransferase
AST	Aspartate Aminotransferase
BMI	Body Mass Index
CATT	Card Agglutination Test for Trypanosomiasis
CI	Confidence Interval
CRF	Case Report Form
CSF	Cerebrospinal Fluid
D	Day
DNDi	Drugs For Neglected Diseases Initiative
DSMB	Data And Safety Monitoring Board
e.g.	Exempli Gratia (For Example)
ECG	Electrocardiogram
EoH	End Of Hospitalisation
EoT	End Of Treatment
g-HAT	Human African Trypanosomiasis due to T.B. Gambiense
H	Hour
HAT	Human African Trypanosomiasis
i.e.	Id Est (That is to say)
ICH	International Conference on Harmonisation
IMP	Investigational Medicinal Product
ITT	Intention To Treat
mAECT	Mini-Anion Exchange Column Test
mAECT-BC	Mini-Anion Exchange Column Test - Buffy Coat
MedDRA	Medical Dictionary For Regulatory Affairs
miITT	Modified Intention To Treat
PK	Pharmacokinetic
PP	Per Protocol
QT	QT interval on ECG (time interval between electrical depolarisation and repolarisation of the left and right cardiac ventricles)
RDT	Rapid Diagnostic Test
SAE	Serious Adverse Event
SAP	Statistical Analysis Plan
T.b.	Trypanosoma Brucei
ULN	Upper Limit of Normal
WBC	White Blood Cell Or White Blood Cell Count
WHO	World Health Organisation
µL	Microlitre

## 4. PROTOCOL

The overall study design, plan description, study objectives, inclusion and exclusion criteria and sample size calculation are described in the Protocol version 2.0 dated of 17/03/2017.

## 5. ANALYSIS SETS AND SUBGROUPS

The analysis sets are the following.

- **Screened HAT positive patients:** all HAT positive patients who signed the informed consent.
- **Intent-to-treat (ITT) population:** all patients included in the study, regardless of whether or not they took the IMP (but the treatment unit was provided to the outpatient);
- **Modified intent-to-treat (mITT) population:** all patients who took at least one tablet of fexinidazole;
- **Evaluable patients:** patients included in the mITT and excluding:
  - Patients lost to follow-up at 18 months (for primary efficacy endpoint and secondary efficacy outcome at 18 month), patients lost to follow-up at 12 months (for secondary efficacy outcome at 12 month), except those who were a failure before being lost to follow-up.
  - Patients with no post-treatment lumbar puncture
  - Patients who died for reasons clearly unrelated to efficacy or safety or disease evolution (\*\*).
- **Per protocol (PP):** all patients who completed the study in accordance with the protocol with no major violations (cf. [Section 8.2](#)) that could interfere with the efficacy evaluation. An out-patient who did not take any tablet of the IMP or with a compliance below 75% of the expected number of tablets is not per protocol unless it is due to lack of tolerance. Premature withdrawal from the study due to treatment inefficacy or intolerance will not be considered as a protocol violation.

Two study cohorts are defined:

- **Inpatients:** patients treated in hospital,
- **Outpatients:** patients treated on an outpatient basis. Note that outpatients that would require hospitalization (for any reason) will be analyzed according to their initial cohort (i.e. as “outpatients”).

The following subgroups are defined according to the stage and severity of disease at inclusion:

- Stage 1
- Intermediate stage
- Stage 1 + Intermediate stage
- Stage 2
- WBC in CSF  $\leq$  100 /  $\mu$ L
- 100 < WBC in CSF  $\leq$  400 /  $\mu$ L
- WBC in CSF  $>$  400 /  $\mu$ L

For the analysis, these subgroups will be calculated as described in Table 1. Subgroups analyses are specified in [Section 8](#).

